### 5.5.8 Procedure in Case of Pregnancy

If a female subject or partner of a male subject becomes pregnant during the study dosing period or within 12 weeks from the discontinuation of dosing, the investigator should report the information in specific forms to the delegated CRO, with timelines as if it is an SAE. Besides completion of the SAE Worksheet, a separate Pregnancy Form should be completed: part A at time of pregnancy reporting and part B when outcome of pregnancy is known. Additional details should be provided in part C during the pregnancy and/or after the delivery.

The expected date of delivery or expected date of the end of the pregnancy, last menstruation, estimated conception date, pregnancy result and neonatal data etc., should be included in this information.

The investigator will follow the medical status of the mother, as well as the fetus and will report the outcome to the sponsor as if the pregnancy is an SAE.

When the outcome of the pregnancy falls under the criteria for SAEs (spontaneous abortion, induced abortion, stillbirth, death of newborn, congenital anomaly [including anomaly in a miscarried fetus]), the investigator should respond in accordance with the report procedure for SAEs. Additional information regarding the outcome of a pregnancy (which is categorized as an SAE) is mentioned below:

- "Spontaneous abortion" includes miscarriage, abortion and missed abortion
- Death of an infant within 1 month after birth should be reported as an SAE regardless of its relationship with the study drug

- If an infant dies more than 1 month after the birth, it should be reported if a relationship between the death and intrauterine exposure to the study drug is judged as "possible" by the investigator
- In the case of a delivery of a living newborn, the "normality" of the infant is evaluated at the birth
- Unless a congenital anomaly are identified prior to spontaneous abortion or miscarriage, the embryo or fetus should be assessed for congenital defects by visual examination

If during the conduct of this study and up to 12 weeks after the EOT visit, the partner of a male subject becomes pregnant, the subject should report the pregnancy to the investigator. The investigator will report the pregnancy to the delegated CRO as an SAE.

### **5.5.9 Emergency Procedures and Management of Overdose**

In the event of suspected roxadustat overdose, the subject should receive supportive care and monitoring. If clinically indicated, phlebotomy may be performed [Section 5.1.5]. The sponsor's medical monitor should be contacted as applicable.

In the event of suspected epoetin alfa or darbepoetin alfa overdose, refer to the SmPCs.

The therapeutic margin of darbepoetin alfa is very wide. Even at very high serum levels, no symptoms of overdose have been observed. In the event of polycythemia, darbepoetin alfa should be temporarily withheld. If clinically indicated, phlebotomy may be performed (see Section 5.1.5).

The therapeutic margin for epoetin alfa is also wide and it has approximately a 3-fold shorter half-life than darbepoetin alfa. Similar to darbepoetin alfa, no specific symptoms of overdose have been observed. In case of polycythemia, same interventions as for darbepoetin alfa should be applied, e.g. temporarily withheld dosing and, if clinically indicated, phlebotomy.

### **5.5.10 Supply of New Information Affecting the Conduct of the Study**

When new information becomes available necessary for conducting the clinical study properly, the sponsor will inform all investigators involved in the clinical study as well as the regulatory authorities. Investigators should inform the IRB/IEC of such information when needed and will inform the subjects. Obtaining renewed signature on an adapted ICF may be required.

## **5.6 Test Drug Concentration**

For evaluation of PK in subjects on HD/HDF and PD (continuous ambulatory peritoneal dialysis [CAPD] and automated peritoneal dialysis [APD]), blood samples will be obtained from roxadustat treated subjects only. The intention is to collect 6 blood samples per roxadustat treated subject at the following time points:

- A. 2 to 0 hours prior to dosing
- B. 1 to 2 hours after dosing
- C. 2 to 3 hours after dosing, at least 60 minutes after sample B
- D. 3 to 5 hours after dosing, at least 60 minutes after sample C
- E. 4 to 6 hours after dosing, at least 60 minutes after sample D
- F. 6 to 10 hours after dosing, at least 2 hours after sample E.

The blood samples can be collected at 1 visit, or over 2 to 3 visits for HD/HDF (as illustrated in [Table 7](#)). The preferred schedule and order of PK visits is a joint decision by the investigator and study subject. For APD subjects, it is recommended to collect all 6 samples in a single visit (as illustrated in [Table 8](#)). For CAPD subjects, all 6 samples must be collected in a single visit (as illustrated in [Table 9](#)). The PK visits should take place between weeks 2 and 8 of the treatment period.

- Samples A, B and C should be collected during the same visit.
- Samples D and E should be collected on the same visit
- Sample F can be collected during the same visit as samples D and E, or during a separate visit. Sample F should be collected as late as possible during the PK visit (last assessment of the visit).

During weeks 1 to 8 subjects treated with roxadustat will be instructed to record the date and time of roxadustat intake in the Study Medication Diary. The information will be used to record the date and time of the roxadustat intake on the occasion prior to PK sampling and the day of PK sampling in the eCRF. The date and time of each PK sample and the actual study drug dose taken on the day of sampling will be recorded in the eCRF.

Sample A should be scheduled on a day when previous study drug intake was less than 3 days prior to the current visit to ensure quantifiable predose samples.

During each PK visit 1 additional sample will be collected for determination of alpha 1-Acid Glycoprotein ( $\alpha$ 1-AGP) and albumin concentration.

#### **Subjects on HD/HDF:**

According to Section [5.1](#) of the protocol, for HD subjects it is recommended that roxadustat is administered any time after completion of dialysis if dosing is scheduled on a dialysis day to avoid potential bias on certain study assessments.

However, at all days when PK sampling is scheduled roxadustat must be taken prior to dialysis start. Roxadustat must be taken at the site for PK visit 1 [Table 7](#).

In addition, at the PK visits, the start and end time of the dialysis should also be recorded in the eCRF.

**Table 7 Examples of Sampling Schedules for Population PK for Subjects on Hemodialysis/Hemodiafiltration**

Schedule †	PK Visit 1	PK Visit 2	PK Visit 3
1	Collect predose sample A. Take roxadustat at site. Start hemodialysis. Collect samples B to E. [Stop hemodialysis.]‡ Collect sample F.	None	None
2	Collect predose sample A. Take roxadustat at site. Start hemodialysis Collect samples B and C. [Stop hemodialysis.]‡	Take roxadustat. Start hemodialysis. Collect samples D to E. [Stop hemodialysis.]‡ Collect sample F.	None
3	Collect predose sample A. Take roxadustat at site. Start hemodialysis Collect samples B and C. [Stop hemodialysis.]‡	Take roxadustat. Start hemodialysis. Collect sample D and E. [Stop hemodialysis.]‡	Take roxadustat. Start hemodialysis. [Stop hemodialysis.]‡ Collect sample F.

† The order of the PK visits for schedule 2 and 3 is a joint decision by the investigator and study subject.

‡ The stop of hemodialysis is independent of blood sample collection. Hemodialysis must not start before roxadustat is taken on PK days.

**Subjects on APD:**

For APD subjects, it is recommended to collect all 6 samples in a single visit. At PK visit 1, roxadustat must be taken at the site. Day-time (manual) PD fluid changes for APD patients are not allowed on the day of PK sampling. In case of subsequent PK visits, roxadustat must be taken after draining the last night-time PD fluid prior to the site visit.

**Table 8 Example of Preferred Sampling Schedule for Population PK for Subjects on APD**

Schedule	PK Visit 1	PK Visit 2	PK Visit 3
1	Collect predose sample A. Take roxadustat at site. Collect samples B to F.	None	None

**Subjects on CAPD:**

*PK sampling*

Subjects on CAPD must complete all PK sampling on a single visit (PK visit 1). Roxadustat must be taken at the site prior to initiation of the first dialysis cycle at the site.

*Dialysate*

Collection of dialysate is to be performed on the same day as PK sampling (roxadustat treated subjects only). For the evaluation of the roxadustat concentration in dialysate, a dialysate sample of 20 mL is collected at the end of the first dialysis cycle at the site. The sample should be withdrawn from the drainage bag after draining the complete volume. The total infused

volume and drained volume of the first dialysis, the start and end time and date of the first dialysis cycle at site and the start time of the second dialysis cycle at site must be recorded in the eCRF. The start time of the dialysis cycle is defined as the start of the infusion of a solution bag into the abdominal cavity and end time is defined as the time when draining of the volume into the drainage bag is completed. All details on the processing of the sample, storage and shipment conditions will be provided in the laboratory manual.

**Table 9 Example of Sampling Schedule for Population PK for Subjects on CAPD**

Schedule	PK Visit 1	PK Visit 2	PK Visit 3
1	Collect predose sample A. Take roxadustat at site. Start first dialysis cycle. Collect samples B to D. Collect dialysate. Start second dialysis cycle at site. Collect samples E to F.	None	None

### 5.6.1 Blood Samples for roxadustat PK Analysis

Samples of venous blood for bioanalysis of roxadustat and related metabolites of roxadustat will be collected into appropriately labeled tubes containing sodium-heparin as anticoagulant.

All further details on the processing of the samples, storage and shipment conditions will be provided in the laboratory manual.

## 5.7 Other Measurements, Assessments or Methods

### 5.7.1 $\alpha$ 1-AGP and Albumin in Serum

Serum levels of albumin and  $\alpha$ 1-AGP will be evaluated as covariates in the PK analysis, since both albumin and  $\alpha$ 1-AGP are involved in plasma protein binding of roxadustat. Serum albumin and  $\alpha$ 1-AGP will be analyzed by the central laboratory using a standardized assay. All details on the processing of the samples, storage and shipment conditions will be provided in the laboratory manual.

### 5.7.2 Hecpidin in Serum

For the determination of hepcidin, serum samples will be drawn at the visits as indicated in Schedule of Assessment. All details on the processing of the samples, storage and shipment conditions will be provided in the laboratory manual.

### 5.7.3 Archival of Serum Samples for Biomarker Analysis

Serum samples will be drawn at the visits as indicated in the Schedule of Assessments. The processed samples will be stored and archived for potential future analysis of relevant biomarkers, linked with the efficacy or safety of the study drugs, prognosis and outcomes. These archival samples will be destructed (if not used in total), maximally 5 years after the last subject completed the study. All details on the processing of the samples, storage and shipment conditions will be provided in the laboratory manual.

#### **5.7.4 Optional Genotyping Sample**

It is now known that roxadustat is a substrate of various transporters as well as metabolizing enzymes. Some of these proteins are polymorphic resulting in different phenotypes in the standard human population. In order to clarify and explain the possible differences observed in the study subjects, exploratory (and optional) genotyping sampling will be included in this study for subjects randomized to the roxadustat arm.

If a separate (optional) informed consent is signed by the subject, a 5 mL whole blood sample for genotyping can be done after randomization, preferably on day 1. The sample will be collected into prelabeled polypropylene collection tubes containing EDTA as anticoagulant. The sample will be taken via venipuncture or cannulation of a forearm vein. The genotyping tube will not require any further processing. Genotyping samples will be stored at -20°C or lower until they are shipped to the delegated CRO and analyzed under the responsibility of Bioanalysis-Europe of Astellas Pharma Europe B.V. All details on the processing of the samples, storage and shipment conditions will be provided in the laboratory manual. The genotyping samples (whole blood and isolated deoxyribonucleic acid) will be managed in strictly secured condition and they will be destroyed maximally 5 years after the last subject completed the study according to relevant guidances and procedures.

#### **5.8 Total Amount of Blood**

The total amount of blood to be collected per subject during the study (screening period, treatment period and the follow-up period) is estimated to be approximately 475 mL.

### **6 DISCONTINUATION**

#### **6.1 Discontinuation of Individual Subject(s)**

A discontinuation is a subject who was enrolled into the study and for whom study treatment is permanently discontinued prematurely for any reason.

The subject is free to discontinue from study treatment or withdraw from the study for any reason and at any time without giving reason for doing so and without penalty or prejudice. The investigator is also free to terminate a subject's involvement in the study at any time if the subject's clinical condition warrants it.

If a subject is discontinued from the study with an ongoing AE or an unresolved laboratory result that is significantly outside of the reference range, the investigator will attempt to provide follow-up until the condition stabilizes or no longer is clinically significant.

Discontinued subjects will complete the EOT visits (EOT visit and EOT + 2 weeks visit) and EOS visit procedures. The appropriate documentation must be entered on the eCRF.

#### **Premature Treatment Discontinuation**

Subjects should be prematurely discontinued from study treatment for any of the following reasons:

- Physician decision that it is in the best interest of the subject to be discontinued from study treatment.
- Significant noncompliance with study procedures, as determined by principal investigator and/or sponsor.
- Pregnancy in a study subject.
- Subject no longer consents to participate in treatment phase of the study.
- Subject receives an organ transplant
- Subject randomized to roxadustat who requires a second course of ESA rescue therapy

If subjects have prematurely discontinued study treatment and have taken at least 1 dose of study drug), they will continue to be followed up at a 6-monthly frequency for the subject's vital status, SAEs and cardiovascular and thromboembolic AEs until their projected date of completion of follow-up period (i.e. projected EOS visit) or until consent withdrawn.

### **Study Withdrawal**

Subjects should be withdrawn from the study for any of the following reasons:

- Subject no longer consents to participate in the study.
- Subject is lost to follow-up despite reasonable efforts by the investigator to contact the subject.

The sponsor may decide to prematurely stop the entire study, e.g. for safety considerations.

## **6.2 Discontinuation of the Site**

If an investigator intends to discontinue participation in the study, the investigator must immediately inform the sponsor. The sponsor may terminate the study at a study site in exceptional circumstances, such as a prolonged period without any enrolments at the site or significant non-adherence to the protocol or GCP requirements.

## **6.3 Discontinuation of the Study**

The sponsor may terminate this study prematurely, either in its entirety or at any study site, for reasonable cause provided that written notice is submitted in advance of the intended termination. Advance notice is not required if the study is stopped due to safety concerns. If the sponsor terminates the study for safety reasons, the sponsor will immediately notify the investigator and subsequently provide written instructions for study termination.

# **7 STATISTICAL METHODOLOGY**

The statistical analysis will be coordinated by the responsible biostatistician of APEB. A Statistical Analysis Plan (SAP) will be written to provide details of the analysis, along with specifications for tables, listings and figures to be produced. As this is an open-label study, the SAP will be finalized prior to accumulation of a substantial amount of data to ensure lack of bias. Any changes from the analyses planned in SAP will be justified in the Clinical Study Report (CSR).

Prior to database lock, a final review meeting of data and Tables/Listings/Figures will be held. Additionally, a meeting to determine analysis set classifications will also take place

prior to database lock. If required, consequences on the statistical analysis will be discussed and documented.

In general, all data will be summarized with descriptive statistics (number of subjects, mean, standard deviation, minimum, median and maximum) for continuous endpoints, and frequency and percentage for categorical endpoints.

## 7.1 Sample Size

The study is sufficiently powered for both regionally-based primary efficacy endpoints. Approximately 750 subjects will be randomized to receive roxadustat or ESA in an open-label fashion in a 1:1 ratio. Randomization will be stratified by the following 5 factors:

- Region (region A versus region B\*)
- Previous ESA treatment (epoetin versus darbepoetin alfa)
- History of cardiovascular, cerebrovascular or thromboembolic diseases (Yes versus No)
- Average prescribed weekly ESA dose in last 4 weeks prior to randomization ( $\leq 200$  IU/kg epoetin or  $\leq 1$   $\mu\text{g}/\text{kg}$  darbepoetin alfa versus  $>200$  IU/kg epoetin or  $> 1$   $\mu\text{g}/\text{kg}$  darbepoetin alfa)
- Screening Hb value ( $\leq 11.0$  g/dL versus  $>11.0$  g/dL)

\* Country assignment to region A and B will be determined based on health care system comparability.

### EU (EMA)

Results from simulations of the EU primary efficacy endpoint in stable dialysis subjects suggest that dosing levels of ESA prior to randomization may play a role in Hb response. Therefore, the EU primary analysis of this study will be tested both in the overall population and in the subgroup of patients defined as subjects with an average prescribed weekly epoetin or darbepoetin dose within the last 4 weeks prior to randomization  $\leq 200$  IU/kg or  $\leq 1$   $\mu\text{g}/\text{kg}$  respectively, following a parametric chain procedure [Millen et al, 2011; Spiessens et al, 2010]. The information fraction will be calculated at the time of database hard lock; it is defined as the number of subjects in the subgroup with respect to the number of subjects in the total study population.

Assuming that the Per Protocol Set (PPS) analysis will consist of 80% of the randomized subjects, 750 randomized subjects will lead to approximately 600 subjects in the PPS. The overall 1-sided significance level (alpha) is fixed at 0.025 and the non-inferiority margin for the EU primary endpoint has been fixed to 0.75 g/dL. The overall alpha will be equally allocated to each of the 2 test populations. If we assume an information fraction of 0.80, this rule will lead to a significance level of 0.0174.

In this setting, 300 subjects for the roxadustat treatment group and 300 subjects for the ESA treatment group will provide 97% power to statistically demonstrate noninferiority of roxadustat versus ESA in the EU primary endpoint in both the total study population and the planned subgroup analysis assuming a difference (roxadustat minus ESA) of -0.25 g/dL in the Hb change from baseline and an SD of 1.5 g/dL. In the case that these assumptions do not hold across the overall population, the planned procedure can still allow for a successful conclusion for the subgroup.

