##### **EU (EMA)**

Results from simulations of the EU primary efficacy endpoint in stable dialysis subjects suggest that dosing levels of ESA prior to randomization may impact Hb response. Therefore, the EU primary analysis of this study will be tested both in the overall population and in the subgroup of patients defined as subjects with an average prescribed weekly epoetin or darbepoetin dose within the last 4 weeks prior to randomization  $\leq 200$  IU/kg or  $\leq 1$   $\mu\text{g}/\text{kg}$  respectively, following a parametric chain procedure (Millen et al., 2011; Spiessens et al, 2010). The information fraction will be calculated at the time of database hard lock; it is defined as the number of subjects in the subgroup with respect to the number of subjects in the total study population.

Assuming that the Per Protocol Set (PPS) analysis will consist of 80% of the randomized subjects, 750 randomized subjects will yield approximately 600 subjects in the PPS. The overall 1-sided significance level (alpha) is fixed at 0.025 and the non-inferiority margin for the EU primary endpoint is set to 0.75 g/dL. The overall alpha will be equally allocated to each of the 2 test populations. If we assume an information fraction of 0.80, this rule will lead to a significance level of 0.0174.

In this setting, 300 subjects for the roxadustat treatment group and 300 subjects for the ESA treatment group will provide 97% power to statistically demonstrate noninferiority of roxadustat versus ESA in the EU primary endpoint in both the total study population and the planned subgroup analysis, assuming a difference (roxadustat minus ESA) of -0.25 g/dL in the Hb change from BL and a standard deviation of 1.5 g/dL. In the case that these assumptions do not hold across the overall population, the planned procedure can still allow for a successful conclusion for the subgroup.

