The overall 1-sided significance level (alpha) is fixed at 0.025. The overall alpha will be equally allocated to each of the 2 null hypotheses defined above. In case of an information fraction of 0.80, this rule will lead to significance level of 0.0174. Following the parametric chain procedure, if at least 1 of both hypotheses is rejected at the significance level of 0.0174, the other 1 can be tested at a significance level of 0.025 while still strongly controlling the overall type I error. The study will be successful for the EU primary efficacy endpoint if either of the null hypotheses is rejected, i.e. if the lower limit of the 2-sided  $100 \times (1 - \alpha^2)\%$  CI for the difference in least square means from the MMRM model is greater than -0.75g/dL.

The EU primary analysis will be tested on the PPS.

The analysis will be repeated on the FAS and ITT as secondary analyses. In addition, an Analysis of Covariance (ANCOVA) model with Last Observation Carried Forward (LOCF) will be used for imputation of missing values (see Section [7.4.1.2](#) for secondary analyses).

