## 7.4.2 Analysis of Key Secondary Endpoints

Once a primary hypothesis has been rejected for the EU primary efficacy endpoint, the secondary endpoints will be tested as described below using a fixed sequence testing procedure.

These tests will be performed only for the overall population in the case that the primary hypothesis was rejected for the overall study population. If the EU primary analysis was not successful for the overall population, but only for the subgroup, then the tests will be performed only for the subgroup. The subgroup population is defined as subjects with an average prescribed weekly epoetin or darbepoetin dose within the last 4 weeks prior to randomization  $\leq 200$  IU/kg or  $\leq 1$   $\mu$ g/kg.

The central laboratory reported Hb values will be used for this analysis.

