4 SAMPLE SIZE

The study is sufficiently powered for both regionally-based primary efficacy endpoints. Approximately 750 subjects will be randomized to receive roxadustat or ESA in an open-label fashion in a 1:1 ratio.

EU (EMA)

Results from simulations of the EU primary efficacy endpoint in stable dialysis subjects suggest that dosing levels of ESA prior to randomization may play a role in Hb response. Therefore, the EU primary analysis of this study will be tested both in the overall population and in the subset (subgroup) of patients defined as subjects with an average prescribed weekly epoetin or darbepoetin dose within the last four weeks prior to randomization ≤ 200 IU/kg or ≤ 1 $\mu\text{g}/\text{kg}$ respectively, following a parametric chain procedure [Millen et al, 2011; Spiessens et al, 2010]. The information fraction will be calculated at the time of database hard lock; it is defined as the number of subjects in the subset with respect to the number of subjects in the total study population.

Assuming that the Per Protocol Set (PPS) analysis will consist of 80% of the randomized subjects, 750 randomized subjects will lead to approximately 600 subjects in the PPS. The overall one-sided significance level (alpha) is fixed at 0.025 and the non-inferiority margin for the EU primary endpoint has been fixed to -0.75 g/dL. The overall alpha will be equally

allocated to each of the two test populations. If we assume an information fraction of 0.80, this rule will lead to a significance level of 0.0174.

In this setting, three hundred (300) subjects for the roxadustat treatment group and 300 subjects for the ESA treatment group will provide 97% power to statistically demonstrate non-inferiority of roxadustat versus ESA in the EU primary endpoint in both the total study population and the planned subset population analysis assuming a difference (roxadustat minus ESA) of -0.25 g/dL in the Hb change from baseline and an SD of 1.5 g/dL. In the case that these assumptions do not hold across the overall population, the planned procedure can still allow for a successful conclusion for the subset population.

US (FDA)

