Table 12 Information Fraction (IF) and One Sided Significance Level (alpha) for the Primary Endpoint

Information Fraction (IF)	alpha (1-sided)
0.5	0.0147
0.6	0.0154
0.7	0.0162
0.8	0.0174
0.9	0.0191
0.97	0.0216

Following the parametric chain procedure, if at least one of the two null hypotheses is rejected at the significance level of 0.0174, the other one can be tested at a significance level of 0.025 while still controlling the overall type I error. The study will be successful for the EU primary efficacy endpoint if either of the null hypotheses is rejected, i.e., if the lower limit of the two-sided $100*(1-\alpha*2)\%$ CI for the difference in least square means from the MMRM model is greater than -0.75g/dL.

If both null hypotheses are rejected, secondary endpoints will be assessed on the overall population. Otherwise, secondary endpoints will not be formally tested.

The covariates will be:

- Previous ESA treatment (epoetin versus darbepoetin alfa);
- Region (region A versus region B);
- History of cardiovascular, cerebrovascular or thromboembolic diseases (Yes versus No)[#];
- Average prescribed weekly ESA dose prior to randomization (≤ 200 IU/kg epoetin or ≤ 1 μ g/kg darbepoetin alfa versus > 200 IU/kg epoetin or > 1 μ g/kg darbepoetin alfa)^{*};
- Baseline Hb value (Continuous).

[#]: This covariate is derived according to a list of cardiovascular disease preferred terms received from the study physician after softlock.

^{*}: For the analyses, the average prescribed weekly ESA dose prior to randomization will be taken from the screening procedure form, in the eCRF. Upon review of data, this covariate was excluded from analysis as number of subjects in the high dose group was too low for the variable to be meaningful.

For these covariates, the IRS value used at randomization will be compared to the eCRF value.

In case of stratification errors during the randomization process, the analysis will use the correct covariates as recorded on the eCRF for the subject.

MMRM model:

An MMRM model will be run for the purpose of implicit imputation of missing data by using all the available information from the observed data via the within-patient correlation

structure. The analysis will be based on the estimated difference between the two treatment arms overall mean effects throughout the evaluation period (weeks 28 to 36) based on this MMRM model.

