7.4.2 Analysis of Key Secondary Endpoints

Once the null hypothesis has been rejected for the EU (EMA) primary efficacy endpoint for both the total population and the subset population, the key secondary endpoints will be tested for the total population, as described below.

The EU (EMA) primary analysis set for the analysis of the key secondary endpoints will be the PPS for the non-inferiority tests and the FAS for the superiority tests.

All inferential analyses will evaluate the difference between the treatment arms: roxadustat versus ESA (i.e. pooled darbepoetin alfa and epoetin alfa).

The key secondary endpoints will be tested using a fixed sequence testing procedure, as depicted in [Table 17](#) in order to maintain the overall one-sided type I error rate for the set of key secondary endpoints at 0.025. If the null hypothesis is rejected for a test, the claim of superiority (or non-inferiority) will be considered successful and the test will progress to the next comparison in sequence as follows:

Table 17 Key Secondary Endpoints Fixed Sequence Testing Procedure

Test	Analysis sets	Endpoint	Comparison
1	PPS	Hb response defined as mean Hb during weeks 28 to 36 within the target range of 10.0 to 12.0 g/dL without having received rescue therapy within 6 weeks prior to and during this 8-week evaluation period.	Non-inferiority of roxadustat versus ESA (the non-inferiority margin for the difference between groups is -15%
2	FAS	Change from BL in Low Density Lipoprotein (LDL) cholesterol to the average LDL cholesterol of weeks 12 to 28.	Superiority of roxadustat versus ESA
3	FAS	Mean monthly IV iron use (mg) during day 1 to week 36 (monthly defined as a period of 4 weeks).	Superiority of roxadustat versus ESA
4	PPS	Change from BL in SF-36 Physical Functioning (PF) sub-score to the average PF sub-score of weeks 12 to 28.	Non-inferiority of roxadustat versus ESA (the non-inferiority margin is fixed as -3)
5	PPS	Change from BL in SF-36 Vitality (VT) sub-score to the average VT sub-score of weeks 12 to 28.	Non-inferiority of roxadustat versus ESA (the non-inferiority margin is fixed as -3)
6	PPS	Change from BL in mean arterial pressure (MAP) to the average MAP value of weeks 20 to 28.	Non-inferiority of roxadustat versus ESA (the non-inferiority margin for the difference between groups is 1 mmHg)

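### At the assumed information fraction of 0.80, the stated 97% EU power holds for the total population but not for the subgroup or for rejecting both hypotheses, where it is about 95%

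*Protocol*

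**What the plan says.** The EU part of Protocol 7.1 claims "97% power to statistically demonstrate noninferiority of roxadustat versus ESA in the EU primary endpoint in both the total study population and the planned subgroup". The synopsis carries the same claim, "in both the total study population and the planned subgroup analysis, assuming a difference (roxadustat minus ESA) of -0.25 g/dL". SAP 4 repeats it for the subset as well as for the whole study: "97% power to statistically demonstrate non-inferiority of roxadustat versus ESA in the EU primary endpoint in both the total study population".

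The subgroup consists of subjects whose prior weekly ESA dose was at most 200 IU/kg epoetin or 1 µg/kg darbepoetin alfa. Protocol 7.1 defines the information fraction as subgroup size over total size and assumes it to be 0.80. "The overall 1-sided significance level (alpha) is fixed at 0.025", split equally between the two hypotheses, which gives 0.0174 for each at that fraction.

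Protocol 7.4.1.1 adds the chain step: once one hypothesis is rejected at 0.0174, "the other 1 can be tested at a significance level of 0.025 while still strongly controlling the overall type I error". EU success requires rejection of either hypothesis.

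The two documents open the key secondary tests differently. Protocol 7.4.2 says: "Once a primary hypothesis has been rejected for the EU primary efficacy endpoint, the secondary endpoints will be tested as described below". SAP 7.4.1.1.1 says: "If both null hypotheses are rejected, secondary endpoints will be assessed on the overall population", with no formal testing otherwise. SAP 7.4.2 agrees with that, requiring rejection "for both the total population and the subset population, the key secondary endpoints will be tested for the total population".

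**The concern.** A single power figure is given for two populations of different size that share the same assumed effect and SD. With 20% fewer subjects, the subgroup must have lower power at the same alpha, so one figure is unlikely to fit both. The wording also invites a joint reading, and joint power cannot exceed the power of the weaker test.

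The subgroup is a confirmatory population, and Protocol 7.1 presents it as the route to success if the assumptions fail overall. Its power should therefore be stated correctly. Under the SAP, the joint figure is also the probability that the key secondary sequence opens at all.

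**Working it through.** **Inputs**

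- From Protocol 7.1: margin 0.75, true difference -0.25, so the distance from the margin is 0.75 - 0.25 = 0.50 g/dL; SD 1.5; 300 per arm in the PPS; information fraction 0.80; overall one-sided alpha 0.025; first-step alpha 0.0174.
- From Protocol 7.4.1.1: second-step alpha 0.025.
- Derived: subgroup size 0.80 × 300 = 240 per arm. This assumes 1:1 allocation within the subgroup, which is reasonable because prior ESA dose is a stratification factor.

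**Reproducing the first-step alpha.** Let A be the total-population test and B the subgroup test. Their statistics have correlation sqrt(0.80). Solving 1 - P(Z_A < c, Z_B < c) = 0.025 gives a one-sided level of 0.01737, which matches the stated 0.0174. The procedure modelled here therefore has the plan's own first-step level.

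**Means of the test statistics**

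- Total: 0.50 / (1.5 × sqrt(2/300)) = 4.0825
- Subgroup: 0.50 / (1.5 × sqrt(2/240)) = 3.6515

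**Single tests, normal approximation**

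| Test | At 0.0174 | At 0.025 |
|---|---|---|
| Total, 300 per arm | 97.6% | 98.3% |
| Subgroup, 240 per arm | 93.8% | 95.5% |

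The total-population entry at 0.0174 is the one that matches the stated 97%; a noncentral-t calculation gives 97.5%. For the subgroup, 95.5% is a ceiling, because no step of the procedure tests it above 0.025. To reach 97% at the full 0.025, the subgroup would need 266 per arm.

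**Chain procedure, exact bivariate normal.** Write P(a, b) for the probability that A is significant at level a and B at level b.

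- P(0.0174, 0.025) = 0.9491
- P(0.025, 0.0174) = 0.9367
- P(0.0174, 0.0174) = 0.9348

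Then:

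- Both rejected: 0.9491 + 0.9367 - 0.9348 = 0.951
- Total rejected: 0.9757 + 0.9367 - 0.9348 = 0.978
- Subgroup rejected: 0.9383 + 0.9491 - 0.9348 = 0.953
- At least one: 0.9757 + 0.9383 - 0.9348 = 0.979

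A simulation of 4 million draws gives 97.8% (total), 95.3% (subgroup), 95.1% (both) and 97.9% (at least one).

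| Result | Stated | Computed | Difference (points) |
|---|---|---|---|
| Total | 97% | 97.8% | +0.8 |
| Subgroup | 97% | 95.3% | -1.7 |
| Both | 97% | 95.1% | -1.9 |

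**Sensitivity to the information fraction**, using the alphas in SAP Table 12:

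| Fraction | Alpha | Power to reject both |
|---|---|---|
| 0.70 | 0.0162 | 92.4% |
| 0.80 | 0.0174 | 95.1% |
| 0.90 | 0.0191 | 96.9% |
| 0.97 | 0.0216 | 97.8% |

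Joint power reaches 97% at a fraction of about 0.91.

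**Access to the key secondaries at 0.80.** The chance that they are not opened is 100 - 95.1 = 4.9% under the SAP rule and 100 - 97.9 = 2.1% under the Protocol rule.

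**The case against.** The strongest reply is that the gap is small and changes no decision. Both shortfalls are under two points, and power of about 95% is ample. The success criterion is rejection of either hypothesis, for which power is 97.9%, and the sentence can be read loosely as describing that procedure. The gap is also smaller than the uncertainty in the planning inputs: an SD of about 1.41 instead of 1.5 would bring the joint figure to 97%. The fraction of 0.80 is itself provisional. It is recalculated at database hard lock, and SAP 7.4.1.1.1 notes that the high-dose group turned out too small to be useful as a covariate, which suggests a realised fraction above 0.80. Finally, the different chances of opening the secondaries come from a conflict between the Protocol and the SAP that exists whatever the power sentence says.

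Most of this stands as a limit on the consequence. It does not make the sentence true. The claim names both populations, so power for either one does not support it. Rounding does not explain the gap, since 95.3% and 95.1% round to 95% and the subgroup ceiling is 95.5%. The sentence is tied to a fraction of 0.80 and an SD of 1.5, and a higher realised fraction does not correct a figure stated for 0.80.

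**Conclusion.** The concern holds. At the plan's own assumptions, 97% is right for the total population and is not met for the subgroup (95.3%) or for rejecting both hypotheses (95.1%). The stated figure is consistent with the total-population power having been applied to both populations. The stated 3% risk of failure becomes 4.7% for the subgroup and 4.9% jointly.

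The effect is limited. EU success is not overstated, and the sample size is adequate. The joint figure governs access to the key secondary tests only under the SAP rule; under the Protocol rule the relevant figure is 97.9%. The result rests on the stated effect and SD applying equally in both populations, on 1:1 allocation within the subgroup, and on a fraction of 0.80.

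**What to change.** In the Protocol synopsis, Protocol 7.1 and SAP 4, replace the power claim with: *Under the parametric chain procedure at an information fraction of 0.80, 300 subjects per arm (240 per arm in the subgroup) provide 97.8% power in the total population, 95.3% in the subgroup, 95.1% to reject both hypotheses and 97.9% to reject at least one.*

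Sample size, alpha and testing procedure stay as they are. The cost is a wording change in three places, and the quoted subgroup and joint figures fall by about two points. Protocol 8.3.3 requires protocol changes to be documented as amendments, so the correction could be made with the next amendment.
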